and impaired functional recovery. Despite good progress in pain management, ineffective postoperative pain management in children remains a global problem. Regional anesthesia is increasingly used in pediatric patients to provide postoperative analgesia and support intraoperative anesthesia. Ultrasound-guided erector spinae plane block (ESPB) is a new approach. First introduced in 2016 by Forero et al., ESPB is a novel regional anesthesia technique that blocks branches of spinal nerves by injecting a local anesthetic into the fascial plane between the erector spinae muscle and the transverse process. Although new, ESPB has become quite popular due to its ease of application and reliability as a relatively superficial block. Initially, ESPB was defined for chronic pain from the thoracic region. Later, its indications expanded and it is now used in both acute and chronic pain conditions. Applications have also been reported in the lumbar, cervical, and sacral regions, respectively. In recent years, an increasing number of randomized controlled trials (RCTs) have reported that it provides effective postoperative analgesia for thoracic surgeries, nephrectomy, inguinal hernia repair, and laparoscopic cholecystectomy operations in children. In our study, we planned to evaluate the effect of bilateral ESPB on intraoperative anesthetic drug consumption and postoperative pain score and analgesia requirement in pediatric patients operated on due to tethered cord syndrome.

2. Objective

In our study, we aimed to reduce intraoperative anesthetic drug consumption and the level of pain in the first 24 hours postoperatively, the need for analgesics, and unwanted side effects related to analgesics by applying bilateral ESPB in pediatric patients operated on due to tethered cord syndrome.

3. Hypothesis

Bilateral ESPB reduces intraoperative anesthetic drug consumption and the need for postoperative analgesia in pediatric patients operated on due to tethered cord syndrome.

4. Study Phase and Nature

Low-risk scientific study - Prospective randomized controlled single-blind clinical trial

5. Study Population

Pediatric patients undergoing surgery for elective tethered cord syndrome

6. Inclusion Criteria

- Patients whose parents consented to participate in the study
- Patients aged 18 and under
- ASA (American Society of Anesthesiologists) physical status I, II, and III
- Pediatric patients undergoing elective tethered cord syndrome surgery

7. Exclusion Criteria

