- Patients whose parents did not consent to participate in the study

- Patients with ASA physical status IV and V

- Use of anticoagulant medications

- Allergy to local anesthetic drugs

- Patients with a history of gastrointestinal bleeding

- Patients with infection in the area where the block is planned

8. Study Center

Health Sciences University Bursa High Specialization Training and Research Hospital Anesthesiology and Reanimation Clinic

9. Study Duration

1 year

10. Material – Method

Patients included in the study will be divided into 2 groups according to the randomized (closed envelope) sampling method; Erector Spina Plane Block (ESPB, n=34) group and Control group (CG, n=34). Patients who regularly take medication due to cardiovascular or other systemic diseases will continue their medication. Those whose coagulation parameters are checked before the operation and are normal will be included in the study.

The patients' age, height, weight, gender, additional diseases, ASA scores, operation and anesthesia duration, operation level, level of block performed in the group undergoing ESP block, and total anesthetic drug consumption will be recorded. Standard ECG, SpO₂, non-invasive blood pressure (invasive blood pressure monitoring in necessary cases), EtCO₂ and BIS monitoring will be applied in the operating room. After appropriate intravenous access is established in both groups of patients, anesthesia induction will be achieved with 2 mg/kg propofol (Propofol 2%®, FreseniusKabi, Melsungen, Germany), 1 µgr/kg fentanyl (Fentanyl Citrate®, Hospira, USA), and 0.6 mg/kg rocuronium (Esmeron®, Organon, Kloosterstraat, Netherlands). Following intubation, anesthesia maintenance will be administered with a 2 l/min flow rate of 50/50 O₂/air mixture. Inhalation anesthetics will not be used, and no additional doses of muscle relaxants will be given. Neuromonitoring will be performed on all patients by the neurosurgical team following intubation. Patients will be turned to the prone position once they are stable. For total intravenous anesthesia in patients undergoing neuromonitoring-based anesthesia maintenance, propofol will be infused at an initial target plasma concentration of 2.5-4 µg.ml⁻¹ (Medcaptain Shenzhen, Guangdong, CHINA, Elevated model FK/FD). Remifentanil (ULTIVA®, GlaxoSmithKline Parma, Italy) will be infused at a rate of 0.5-1 µg/kg/min. Infusions will be maintained to maintain a BIS of 40-60. Preoperative,

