peroperative 5th, 10th, 15th, 30th, 60th, 90th, 120th, 180th minute, and post-extubation heart rate, supravascular pressure, intravascular pressure, SpO₂, ETCO₂, and BIS values will be recorded.

Patients will be randomly assigned to two separate groups using a sealed envelope method, regardless of their demographic and surgical characteristics. In the ESP Block group, with the patient in the prone position, the research anesthesia team, following aseptic and antiseptic rules, will insert a linear probe (Hitachi Aloka Prosound F31) with a depth of 2-4 cm and a frequency of 10-15 mHz, approximately 2-3 cm lateral to the spinous process, one level above the operative level, in the parasagittal plane, under USG guidance (Hitachi Aloka Prosound F31). After visualizing the transverse process using an in-plane approach, a 50 mm long block needle (Braun Stimuplex® D 0.22 Gax2 in.50mm, Braun, Germany) will be inserted through the skin, passing through the trapezius and erector spinae muscles. When the needle reaches the transverse process (approximately 2-3 cm deep), a test dose of 0.5-1 mL of 0.9% NaCl will be administered between the erector spinae fascia and the vertebral transverse process to confirm the needle's position. After the fascia is seen to be open, a local anesthetic volume of 0.5% bupivacaine (Buvasin, VEM Pharmaceuticals, Turkey) will be calculated as 2 ml per vertebral pressure, not exceeding a maximum dose of 2 mg/kg. This total volume will be diluted half and half with 0.9% NaCl solution to prepare a 0.25% bupivacaine concentration. The calculated local anesthetic solution will be administered to the erector spinae area for ESPB. The same procedures will be performed on the opposite side. No procedure will be performed on the control group. Both groups will receive 15 mg/kg Paracetamol (Parol®, ATABAY, Kurtköy, Pendik, İstanbul) intravenously 20 minutes before the end of surgery. After surgery, patients will be decurarized with 2 mg/kg IV sugammadex (Bridion, MerckSharpDohme, New Jersey, USA), extubated, and taken to the recovery unit. After being admitted to the recovery room, both groups will be assessed using the Wong-Baker FACES™ Pain Rating Scale for children under 5 years old and the FLACC: Pain Rating Scale for children 5 years and older, with pain scores at 0, 5, 10, 15, and 20 minutes. Patients with scores >5 will receive 0.5 mcg/kg fentanyl (TALİNAT®, VEM İlaç, Kapaklı/TEKİRDAG) for rescue analgesia. Paracetamol 15 mg/kg/6 hours will be administered intravenously for postoperative analgesia. A blinded investigator will assess patients' pain scores, analgesic requirements, names of analgesics administered, and nausea/vomiting at 30 minutes, 1, 2, 4, 6, 12, and 24 hours postoperatively. The time and dose of the first postoperative analgesic, and length of hospital stay will be recorded.

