
11. Research Budget

The cost of 34 block needles and 34 doses of the drug buvasin containing the active ingredient bupivacaine for one patient has been submitted with a propharmaceutical invoice. The expenses will be covered by the researchers.

12. Ethics Committee Approval

An application has been submitted for ethics committee approval.

13. Statistics

Statistical analyses of the obtained data will be performed using the IBM SPSS Statistics 21.0 software package. Descriptive statistics of the data will include mean, standard deviation, frequency, and percentage values. Chi-square and FischerExact tests will be used for the analysis of categorical variables. The normality assumption of continuous numerical variables will be checked separately in groups using the Shapiro-Wilk test. Analysis of variance (ANOVA) will be used for independent group

comparisons of numerical variables showing normal distribution. Kruskal-Wallis (KW) test will be used for variables that do not show normal distribution. For comparisons of consecutive measurements, the Wilcoxon Signed Ranks test will be used for pairs of measurements, the Friedman test for more than two measurements, and the Pearson correlation test will be used as a correlation test. The significance level will be set at $p<0.05$ in all analyses. The required sample size for the study was calculated as 68 (34+34) patients in total, including the group that underwent ESPB and the group that did not undergo ESPB, with an effect size of 0.70, 80% test power, and 95% confidence level. The relevant calculations were made in the G-Power 3.1.9.2 software package.

14. References

1. Gado, A. A., Alsadek, W. M., Ali, H., & Ismail, A. A. (2022). Erector spinae plane block for children undergoing cardiac surgeries via sternotomy: a randomized controlled trial Anesth Pain Med. 2022;12(2):e123723. doi: 10.5812/aampm-123723. PMID: 35991776
2. Aksu, C., & Gürkan, Y. (2018). Ultrasound guided erector spinae block for postoperative analgesia in pediatric nephrectomy surgeries. J Clin Anesth. 2018 Mar;45:35-36 doi: 10.1016/j.jclinane.2017.12.021. Epub 2017 Dec 20. PMID: 29274546

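### Section 13 compares the arms with no baseline covariate, giving up precision that the recorded age and weight could supply

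*Combined protocol and SAP*

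**What the plan says.** **Population.** Section 6 admits "Patients aged 18 and under" and sets no lower limit.

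**Allocation.** Section 10 describes 34 patients per arm and states: "Patients will be randomly assigned to two separate groups using a sealed envelope method, regardless of their demographic and surgical characteristics".

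**Outcomes.** Section 10 measures pain with "the Wong-Baker FACES™ Pain Rating Scale for children under 5 years old and the FLACC: Pain Rating Scale for children 5 years and older". It also says that "total anesthetic drug consumption will be recorded", and gives no per-kg or other scaling.

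**Baseline data.** The recorded variables include "age, height, weight, gender, additional diseases, ASA scores, operation and anesthesia duration, operation level".

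**Analysis.** In Section 13, "Analysis of variance (ANOVA) will be used for independent group" comparisons of normally distributed variables, and Kruskal-Wallis otherwise. Categorical variables go to chi-square or Fisher's exact test. No covariate, stratum or separate analysis by pain scale is named for any arm comparison. A Pearson correlation is listed, but it does not adjust the arm contrast.

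**Sample size.** Section 13 gives 68 patients (34+34) for an effect size of 0.70, 80% power and 95% confidence. It does not name the outcome behind 0.70, its SD, or whether it is an unadjusted effect.

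**The concern.** Two features of this trial make age and body size likely to drive the outcomes. Children on either side of age 5 are scored on different instruments, so age band may shift the recorded pain score whatever the treatment. Drug totals rise with body weight, and weight varies widely when infants and adolescents are pooled.

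Neither the allocation nor the analysis uses this information. Between-child spread due to age and weight therefore stays in the error variance and widens the confidence interval. If the arms happen to differ in the share of under-5s or in mean weight, the estimated block effect is not corrected for it. The variables needed are already on the case record, so the loss is avoidable.

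**Working it through.** **1. The plan's own figure.** Inputs from Section 13: d = 0.70, two-sided alpha 0.05 (sidedness is not stated; two-sided reproduces the plan), n = 34 per arm. For a two-sample t-test the noncentrality is d × √(n/2) = 0.70 × √17 = 2.886 with 66 df, which gives power 81.2%. With 33 per arm power is 79.97%, just short of 80%, so 34 per arm and 68 in total reproduce exactly.

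**2. Power with adjustment.** If the covariates explain a share R² of outcome variance, the effective effect size is 0.70/√(1−R²), with 64 df for two covariates. The documents give no R², so these values are assumed:

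| R² | Effective d | Power at 34 per arm |
|---|---|---|
| 0 (planned test) | 0.700 | 81.2% |
| 0.05 | 0.718 | 83.1% |
| 0.10 | 0.738 | 85.0% |
| 0.20 | 0.783 | 88.8% |
| 0.30 | 0.837 | 92.5% |
| 0.50 | 0.990 | 98.0% |

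Two covariates that explain nothing lower power only from 81.16% to 81.13%, through the two lost degrees of freedom.

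**3. Validity of the planned test.** In 20,000 simulated null trials for each of R² = 0.1, 0.3 and 0.5, the unadjusted test rejected in 4.9% to 5.3%. Among those trials in which a continuous covariate differed by at least 0.3 SD between arms, it rejected in about 7%, 12% and 16% respectively. By the normal approximation, a difference that large occurs in about 22% of trials.

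**4. Chance imbalance in age band.** With K under-5s among 68 and arms fixed at 34/34, the number in one arm is hypergeometric(68, K, 34). The difference between arms has the same parity as K, so a threshold of 5 acts as 6 whenever K is even. I therefore use 6 or more. The documents do not give K. Assumed values give:

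- K = 14: 13.2%
- K = 20: 18.3%
- K = 27 or 41: 13.6%
- K = 34: 22.5%

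This is about 13% to 23% at these counts. Over every count from 14 to 41 the lowest value is 7.7%, at K = 15. A difference of 6 is 6/34 = 17.6 percentage points.

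**5. Weight and raw drug totals.** Write log total = log weight + log per-kg use, with the two parts independent. Assume uniform weights and a 25% spread in per-kg use, so that its log variance is about 0.25² = 0.0625.

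- 10 to 40 kg: variance of log weight 0.146; share 0.146/(0.146 + 0.0625) = 70%.
- 5 to 60 kg: variance of log weight 0.388; share 0.388/(0.388 + 0.0625) = 86%.

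**The case against.** The strongest reply is that nothing here is an error. Unstratified randomisation followed by an unadjusted test is a valid design, the protocol discloses the choice, and the sample size is arithmetically right. The p-value and confidence interval already allow for chance imbalance. All of this stands.

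Two stronger readings are tempting, and the documents support neither.

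- A reader might infer that the arm comparison is biased, or that an imbalance would be mistaken for a block effect at an inflated error rate. Over all randomisations there is no bias, and the error rate is about 5%. The higher rates in step 3 apply only to trials that happen to be imbalanced.
- A reader might infer that the trial is underpowered. If 0.70 were a covariate-adjusted effect, the planned test would have 77%, 66% or 52% power at R² of 0.1, 0.3 or 0.5. If 0.70 came from unadjusted data in a similarly wide age range, the noise is already inside the planned 80%, and adjustment is a gain rather than a repair. The documents do not say which applies.

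It is also fair to object that the harm from age-band imbalance is not shown to be large. If the two scales differed by 1 point at equal pain (assumed), 6 extra under-5s in one arm would move the difference in means by 6/34 × 1 = 0.18 points. The documents give no offset or SD against which to judge that. At low R² the power gain is only 2 to 4 points.

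None of this is a reason to leave the covariates out, since including them costs almost nothing.

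**Conclusion.** The point holds as one of precision and robustness, not of validity. The planned comparisons ignore recorded baseline variables that are likely to matter here. They therefore forgo power and leave any chance imbalance in age band or weight unadjusted in the estimate.

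The size depends on quantities that the documents do not give. For pain scores the gain runs from slight to large according to R², and the lower end is as plausible as the upper on this text. The case is stronger for drug consumption, because totals with no stated scaling mix infants with adolescents. The 70% to 86% share rests on the assumed weight ranges and per-kg spread, and applies to the log of the total.

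Adjusting for age band removes an average offset between the two pain scales. It does not make them interchangeable.

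**What to change.** **Main change, in Section 13.** Pre-specify the following:

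- Pain scores: a linear model (ANCOVA) with arm and age band (under 5; 5 and older, matching the scale change), or a van Elteren rank test stratified by age band if the scores are skewed. Also show pain results within each age band.
- Drug consumption: analyse per kg, or model the log total with arm, log weight and age band.
- Analgesic need as yes/no: a Mantel-Haenszel comparison stratified by age band.
- Report adjusted differences with 95% confidence intervals.

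This costs a few sentences. It needs no extra patients, data or change to allocation, so it can still be made if enrolment has begun, provided that it is fixed before the outcome data are compared by arm. Naming the covariates now also prevents a choice made after an imbalance is seen.

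**Optional, only if enrolment has not begun.** Stratify the envelopes by the same age band, with small permuted blocks in each stack. The blocks are essential. In simulation, two unblocked stacks still left a difference of 5 or more under-5s in about 18% to 31% of trials, and final arm sizes more than 2 apart in 58% to 61%. The cost is a second stack, and each arm may end a patient or two away from 34. With blocks of four, for example, each stack can finish at most 2 out of balance, so the arms differ by at most 2 + 2 = 4 (36 against 32).

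### Section 10 does not say that the 2 mg/kg bupivacaine maximum covers both sides; followed literally, the sequence allows up to 4 mg/kg in a small child

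*Combined protocol and SAP*

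**What the plan says.** The rule is in Section 10 (Material – Method). After describing probe, needle and saline test dose on one side, the text says that the volume of 0.5% bupivacaine "will be calculated as 2 ml per vertebral pressure, not exceeding a maximum dose of 2 mg/kg". It goes on: "This total volume will be diluted half and half with 0.9% NaCl solution to prepare a 0.25% bupivacaine concentration". Then: "The calculated local anesthetic solution will be administered to the erector spinae area for ESPB. The same procedures will be performed on the opposite side".

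There is one injection site on each side, "one level above the operative level, in the parasagittal plane", so the number of levels in the volume rule is not the number of injections. Which levels count is not stated.

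Two other places bear on the point. Section 11 (Research Budget) prices "34 block needles and 34 doses of the drug buvasin containing the active ingredient bupivacaine for one patient", without giving the size of a dose; the ESPB arm has 34 children. Section 6 (Inclusion Criteria) admits "Patients aged 18 and under" and sets no lower limit of age or weight.

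**The concern.** A weight-based maximum needs a stated unit, and in a bilateral block that unit is either the side or the child. Here the calculation, the maximum and the injection all come before the second side is mentioned, and the second side is covered only by an instruction to repeat. No sentence halves the amount or says that the limit is a total for both sides.

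If the sponsor means 2 mg/kg per child, an anesthetist who repeats the whole sequence exceeds that limit in a small child while following the text. If the sponsor means 2 mg/kg per side, the plan permits up to 4 mg/kg without saying so. Small children are expected: besides the open lower age limit, Section 10 assigns a "Pain Rating Scale for children under 5 years old".

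**Working it through.** The plan derives no figure for the maximum, so there is none to reproduce. Its dilution is consistent: 0.5% mixed half and half with saline gives 0.25%. The volume doubles and the milligrams do not change.

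**Inputs from Section 10**
- 0.5% bupivacaine is 5 mg/ml, so 2 ml is 2 × 5 = 10 mg.
- 0.25% is 2.5 mg/ml.
- The maximum is 2 mg/kg.
- There are two sides.

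**Interpretation and assumptions**
- The printed word pressure is read as vertebral level. This interprets garbled text, and every threshold below depends on it.
- L (levels counted) and W (weight in kg) are assumed and shown over a range.

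**Three readings of the total dose in mg**
- A, volume rule and maximum both for the two sides together: min(10L, 2W).
- B, volume rule per side, maximum for the two sides together: min(20L, 2W).
- C, volume rule and maximum both per side: 2 × min(10L, 2W).

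A and B never exceed 2 mg/kg. C exceeds 2W when min(10L, 2W) > W, that is when W < 10L. C equals 4W when 2W ≤ 10L, that is when W ≤ 5L.

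| L | W (kg) | A (mg) | B (mg) | C (mg) | C (mg/kg) |
|---|---|---|---|---|---|
| 1 | 5 | 10 | 10 | 20 | 4.0 |
| 1 | 8 | 10 | 16 | 20 | 2.5 |
| 1 | 10 | 10 | 20 | 20 | 2.0 |
| 2 | 10 | 20 | 20 | 40 | 4.0 |
| 2 | 15 | 20 | 30 | 40 | 2.7 |
| 2 | 20 | 20 | 40 | 40 | 2.0 |
| 3 | 15 | 30 | 30 | 60 | 4.0 |
| 3 | 20 | 30 | 40 | 60 | 3.0 |
| 3 | 25 | 30 | 50 | 60 | 2.4 |
| 3 | 30 | 30 | 60 | 60 | 2.0 |
| 4 | 20 | 40 | 40 | 80 | 4.0 |
| 4 | 40 | 40 | 80 | 80 | 2.0 |

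**Sensitivity.** If the 2 ml meant the diluted solution, each level would carry 2 × 2.5 = 5 mg and the thresholds would halve: above 2 mg/kg below 5L kg, and 4 mg/kg at or below 2.5L kg. The 4 mg/kg total is still reached, for example at 2 levels and 5 kg (20 mg) or 4 levels and 10 kg (40 mg).

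**Volume per side.** With the maximum as a total, the limit per side is 1 mg/kg ÷ 2.5 mg/ml = 0.4 ml/kg of the 0.25% solution. In general the volume per side is total ÷ 2 ÷ 2.5. At 3 levels, B against C gives 6 against 12 ml at 15 kg, 8 against 12 ml at 20 kg, 10 against 12 ml at 25 kg, and 12 ml for both at 30 kg.

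**The case against.** The strongest reply is that the two readings are not equally likely, and this stands. Section 10 gives its other weight-based boluses per patient without saying so: propofol 2 mg/kg, fentanyl 1 µg/kg, rocuronium 0.6 mg/kg, paracetamol 15 mg/kg, sugammadex 2 mg/kg. An unqualified maximum in mg/kg fits that convention. The sentence on dilution calls the amount a total volume, and the budget has one dose per ESPB child. The instruction to repeat can be taken to mean the probe, needle, test dose and injection only.

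None of this settles the matter. The total volume is the one just calculated, before the second side appears, so it may be the sum over levels on one side. A budget line without milligrams or milliliters cannot define a limit.

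It is also fair that this is one clinic, that a research anesthesia team does the blocks, and that the team may share one practice. Nothing in the documents shows that operators disagree.

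A reader might go further and infer that the plan prescribes 4 mg/kg, that such a dose is toxic, or that children are left unwatched. The documents support none of these. The per-child reading is the better supported one. No dose limit other than the 2 mg/kg is given, so harm between 2 and 4 mg/kg is not shown. And ECG, blood pressure, SpO₂, EtCO₂ and "BIS monitoring will be applied in the operating room", with values recorded to 180 minutes and after extubation.

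**Conclusion.** The point holds as an unstated unit on a pediatric dose maximum. A per-child limit is probably what is meant, but the sequence as written can be followed to a total of up to 4 mg/kg, twice the stated figure. The gap concerns small children only: the two ways of applying the maximum part below 10 kg per level and are a factor of two apart at or below 5 kg per level. In heavier children the volume rule governs and the total stays at or below 2 mg/kg on any reading. At 15 kg with 1 level, for example, even the per-side total is 20 mg, or 1.3 mg/kg.

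These sizes rest on reading pressure as level and on assumed weights and levels; how many children would be affected cannot be computed from the documents. A reader might also infer bias in the trial's results. That does not follow, because the ambiguity concerns what the ESPB arm receives and does not affect how the arms are formed or compared. The change is cheap and should be made.

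**What to change.** Add one clause to Section 10: 2 mg/kg is the maximum bupivacaine dose for both sides together, with half given on each side, so at most 1 mg/kg (0.4 ml/kg of the 0.25% solution) per side. If 2 mg/kg on each side is intended, state the total as 4 mg/kg and justify it.

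Let the team say what the 2 ml per level refers to, and do not default to 2 ml per level on each side. For a team that now counts it for both sides together (reading A), that default (reading B) would raise the total: at 3 levels from 30 to 40 mg at 20 kg, and from 30 to 60 mg at 30 kg. Both stay within 2 mg/kg, but a clarification made for safety should not raise the dose unnoticed.

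The cost is in volume. Compared with giving the full maximum on each side, the volume per side falls by up to half in children below 10 kg per level, which may limit spread. If the team means 2 ml per level for both sides together, the volume per side is half that of reading C at every weight. A team that already treats 2 mg/kg as the total, and keeps its own volume rule, writes down what it does. Sample size and analysis stay as they are.

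### Section 10 assigns the two pain scales to the wrong age groups: self-report FACES to under-5s, observer-scored FLACC to children 5 and older

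*Combined protocol and SAP*

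**What the plan says.** Section 10 (Material – Method) fixes the pain instrument by age on arrival in the recovery room: "Wong-Baker FACES™ Pain Rating Scale for children under 5 years old and the FLACC: Pain Rating Scale for children 5 years and older". Five recovery-room assessments are scheduled, the first on arrival and the last 20 minutes later. A score above 5 on either scale leads to rescue fentanyl.

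Later in the same section a blinded investigator records "pain scores, analgesic requirements, names of analgesics administered, and nausea/vomiting at 30 minutes, 1, 2, 4, 6, 12, and 24 hours postoperatively". That sentence names no scale.

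Section 6 (Inclusion Criteria) admits "Patients aged 18 and under", with no lower limit, and no exclusion criterion in Section 7 removes infants or preverbal children.

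On the role of the pain score:
- Section 2 (Objective) aims to reduce "the level of pain in the first 24 hours postoperatively".
- The Introduction says the study will evaluate "intraoperative anesthetic drug consumption and postoperative pain score and analgesia requirement".
- Section 3 (Hypothesis) is narrower: "Bilateral ESPB reduces intraoperative anesthetic drug consumption and the need for postoperative analgesia".

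No primary endpoint is named.

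**The concern.** The two scales work in different ways. On Wong-Baker FACES the child looks at a row of faces and chooses one, so the child must understand the task. On FLACC an observer rates face, legs, activity, cry and consolability, so the child need do nothing. The protocol describes neither tool; this is general knowledge of what the instruments are, not a figure from a cited source. As written, the tool that needs the child's cooperation goes to the only age band containing preverbal children, and the tool designed to do without it goes to the band that can mostly self-report. Both halves are reversed, so this is more than a dispute about the exact age cut.

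Pain level over 24 hours is a stated objective. Scores that a child cannot give will be missing, or will be filled in by someone guessing at a face, and neither can be repaired after collection. Because the score also triggers rescue fentanyl, some of the error may carry into postoperative analgesic use, which is part of the Hypothesis. Intraoperative drug consumption is not affected.

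**Working it through.** **The plan's own figure.** Section 13 gives 68 patients (34 + 34) for an effect size of 0.70, 80% power and a 95% confidence level. A two-sided two-sample t-test at alpha 0.05 needs 33.02 per arm, rounded up to 34, so 68 in total, with power 81.2% at 34 per arm. The figure reproduces. It does not help to size this point, because Section 13 does not say which outcome the 0.70 refers to.

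**Is the assignment inverted?** Setting the sentence against the nature of each tool:

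| Age band | Scale assigned in Section 10 | Who produces the score | Consequence if followed literally |
|---|---|---|---|
| Under 5 | FACES | The child | Preverbal children cannot complete it; some 3–4-year-olds may manage |
| 5 and older | FLACC | An observer | A score is obtained, but self-report is given up |

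No other section reverses or qualifies the split, names another scale, or says how to score a child who cannot self-report.

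**Where the rule applies.** Inputs: the assessment times in Section 10 and the sample size in Section 13.

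- Recovery room: 0, 5, 10, 15, 20 minutes = 5 assessments, scale named.
- Later: 30 minutes, 1, 2, 4, 6, 12, 24 hours = 7 assessments, scale not named.
- Per patient: 5 + 7 = 12.
- Planned scores: 68 × 12 = 816.
- Scale explicit: 68 × 5 = 340, or 5/12 = 41.7%.
- Scale not named: 68 × 7 = 476, or 7/12 = 58.3%.

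All 68 patients fall in one band or the other. The 476 later scores are covered only if the same two scales are carried forward. That is the natural reading, since the protocol offers no others, but it is an inference.

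**What cannot be computed.** These counts show where the sentence applies, not how many scores would be lost or degraded. Loss of scores can arise only among under-5s who cannot use FACES, and the protocol gives neither their expected number nor any age distribution. A figure for lost power would need an assumed missing fraction and the further assumption that the 0.70 refers to a pain score, so none is offered.

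**Direction.** Both arms follow the same age rule, so the expected effect is missing data and noise, not a systematic difference between arms.

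**The case against.** The strongest reply is that this is a translation slip and not a design decision. Section 10 itself contains the terms "supravascular pressure, intravascular pressure", apparently for systolic and diastolic pressure; the title garbles the name of the block, and the first section heading is left untranslated. Two exchanged scale names fit that pattern, and every harm described depends on staff following the sentence as written. This stands as a possibility, and the text cannot settle it. It does not remove the need to correct the sentence: the written rule is what assessors and readers have, and an uncorrected swap would leave readers unsure which scale was used.

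Four narrower objections also have force.

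- The counts cover older children's FLACC scores, which would be obtained and are not invalid, so they must not be read as a count of damaged scores.
- The explicit rule covers only the first 20 minutes in recovery, soon after extubation, when observer scoring of an older child costs some information but is defensible.
- The Hypothesis does not name the pain score, and no bias between arms is expected.
- The point relies on knowledge of the instruments that the protocol does not supply. What the tools are is not in dispute, but the exact age at which FACES becomes usable is not settled by the document.

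These limit the importance of the point. None makes the sentence correct.

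**Conclusion.** The concern holds. As written, Section 10 assigns each pain scale to the wrong age group, and with no lower age limit the protocol allows enrolment of children who cannot complete the scale they are given. The supported consequence is missing or noisy pain scores of unknown extent in a stated objective, with possible carry-over to rescue analgesic use.

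Confidence is high that the sentence is inverted. Whether the design or only the wording is at fault is unknown. The consequences rest on two assumptions: that the sentence is followed literally, and that some children too young to self-report are enrolled. Extension beyond 20 minutes further assumes that the same scales are used later. This should be fixed before scores are collected.

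**What to change.** Confirm with the authors whether the two scale names were exchanged. Then correct the sentence in Section 10, keeping the protocol's own age cut: observer-scored FLACC for children under 5 and for any older child who cannot self-report, and self-reported Wong-Baker FACES for children 5 and older. Add a clause stating that the same assignment applies at the 30-minute to 24-hour assessments, and bring the case report form into line.

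Because a score above 5 triggers rescue, the authors should reconcile that passage with the corrected assignment. No view is taken here on the rescue rule.

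Optionally, report pain scores by scale and age band as a supportive analysis, using the tests already listed in Section 13.

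The cost is one corrected sentence, one clarifying clause and a matching form. No extra patients, staff, procedures or software are needed.
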